1 INTRODUCTION

1.1 Objectives of Statistical Analysis Plan

The statistical analysis plan (SAP) describes in detail the statistical analyses to be conducted on the data from the Phase 1 trial I8B-MC-ITST.

The SAP elaborates on the statistical analyses outlined in the protocol, and any deviations are clearly stated in the present SAP including the reason for the deviation. The trial will be evaluated according to the specifications given in this analysis plan. However, deviations from the SAP may be necessary in which case the nature of and the reason for the deviations will be documented and explained in the clinical study report (CSR).

1.2 Scope

This SAP is based on the finalized protocol Version 2.0, dated 17-Jan-2020.

Statistical Analysis Plan				
Trial ID	EudraCT-No.	Date	Status / Version-No.	Page
I8B-MC-ITST	2019-003493-13	15 Jul 2020	Final 1.0	10 of 47

2 STUDY OBJECTIVES AND ENDPOINTS

The purpose of this study is to compare the time to recovery from hyperglycemia following LY900014 administration in comparison to Humalog® in a similar situation as when a subject experiences hyperglycaemia by forgetting to deliver a bolus when consuming a meal or when there is suspension of insulin delivery e.g. due to a malfunction of the insulin pump in subjects with Type 1 Diabetes Mellitus (T1DM).

Table 1 shows the objective and endpoints of the study.

Table 1 Objectives and endpoints

Objectives

Primary

- To compare the time to recovery from hyperglycaemia following a missed meal bolus with LY900014 vs. Humalog®, given as a correction bolus via pump infusion
- To compare the time to recovery from hyperglycaemia following basal insulin suspension with LY900014 vs. Humalog®, given as a correction bolus via syringe injection

Secondary

- To compare the pharmacodynamics and insulin lispro pharmacokinetics following a correction bolus of LY900014 vs. Humalog® during recovery from hyperglycaemia following a missed meal bolus.
- To compare the pharmacodynamics and insulin lispro pharmacokinetics following a correction bolus of LY900014 vs. Humalog® during recovery from hyperglycaemia after basal insulin suspension.

Endpoints

PD endpoints:

- Time to recovery from hyperglycemia (time of correction bolus to time when plasma glucose [PG]) = 140 mg/dL)

PK endpoints:

- t_{max} , time to maximum observed insulin concentration.
- Early 50% t_{max} , time to half-maximum before C_{max} .
- $AUC_{(0-15min)}$, are under the insulin curve from 0 to 15 minutes.
- $AUC_{(0-30min)}$, are under the insulin curve from 0 to 30 minutes.

PD endpoints:

- $AUC_{(B-tPG140)}$, area under the PG curve but above 140 mg/dL from time of correction bolus (B) to time when PG is 140 mg/dL)
- $AUC_{(B-tPG180)}$, area under the PG curve but above 180 mg/dL from time of correction bolus (B) to time when PG is 180 mg/dL)

Statistical Analysis Plan				
Trial ID	EudraCT-No.	Date	Status / Version-No.	Page
I8B-MC-ITST	2019-003493-13	15 Jul 2020	Final 1.0	11 of 47

Objectives

Exploratory

- To assess the blood glucose response after basal insulin suspension for LY900014 vs. Humalog[®].

Safety

- To assess the safety and tolerability of LY900014 and Humalog[®].

Endpoints

- Rate of change in PG (the change in PG at the time of bolus IMP administration to PG = 140 mg/dL measurement divided by the duration of time for this interval)
- PG_{max}, maximum observed plasma glucose
- Time to hyperglycaemia (PG > 240 mg/dL) after basal insulin suspension
- Peak ketone concentration after basal insulin suspension

Safety endpoints:

- AEs

Safety assessments:

- Hypoglycaemic episodes
- Laboratory safety parameters
- Physical examination
- Vital signs
- ECG

Statistical Analysis Plan				
Trial ID	EudraCT-No.	Date	Status / Version-No.	Page
I8B-MC-ITST	2019-003493-13	15 Jul 2020	Final 1.0	12 of 47

3 STUDY DESIGN AND DESCRIPTION

3.1 Study Design

The study is a phase 1, single-centre, randomised, 2-treatment, subject- and investigator-blind, 2-way cross-over trial in subjects with T1DM. The trial will be carried out in one center in Germany.

The study consists of a:

- informed consent (Visit 0)
- a screening visit (Visit 1)
- two in-house study visits with IMP administration (Visits 2 and 3)
- a follow-up (FUP) visit (Visit 4)

Figure 1 shows the study design of the study.

The information visit will take place at least 1 day prior to the screening visit in order to obtain the subjects informed consent. The subjects will attend the screening visit 1–28 days prior to Visit 2 to determine their eligibility. After screening, all eligible subjects will, in random order, undergo two in-house study visits. Each in-house visit will comprise a 3-day stay at the trial site. The in-house visits will be separated by a wash-out period of 3–14 days (between Visit 2, Day 2 and Visit 3, Day 1). Each subject will be randomised to a treatment sequence consisting of two treatments, i.e. LY900014 and Humalog[®], to be administered at the two separate in-house study visits. Randomisation will take place on Day -1 of Visit 2.

At each of the two in-house visits, subjects will arrive at the trial site in the afternoon of Day -1. Subjects' infusion set and reservoir of the insulin pump will be changed at the trial site and filled with either LY900014 or Humalog[®] according to the randomisation list. Subjects who are not using a Medtronic 640G insulin pump will be provided with a Medtronic 640G insulin pump and will be trained in its use. Users of this pump may use their own pump for the experimental procedures. The subject's usual basal rate settings will be programmed in the study pump and the basal rate infusion will be started.

Day -1 / Day 1: recovery from hyperglycemia after missed meal bolus

In the evening of Day -1, subjects will receive a pre-defined evening meal. The subjects will cover the meal with a bolus of IMP. Overnight, the basal insulin infusion rate will be running and a target fasting plasma glucose level in the range of 126 ± 20 mg/dL will be aimed for. A single hourly basal rate will be started from at least – 3 hours prior to meal ingestion. At approx.

Statistical Analysis Plan				
Trial ID	EudraCT-No.	Date	Status / Version-No.	Page
I8B-MC-ITST	2019-003493-13	15 Jul 2020	Final 1.0	13 of 47

08:00 hours on Day 1, a standard liquid meal [REDACTED] will be provided. No bolus insulin will be administered with the aim to induce postprandial hyperglycemia (PG > 240 mg/dL). On-site glucose measurements [REDACTED] will be performed regularly and frequently after meal ingestion. As soon as a glucose measurement above the high glucose threshold (PG > 240 mg/dL) has been measured and the result has been confirmed by a second measurement, a correction bolus will be administered with the aim to bring the subject's glucose level down to $PG \leq 140$ mg/dL. Regular and frequent sampling for glucose on-site analysis continues and the time to reach the euglycemic range threshold will be documented. PK and glucose measurements will be collected until 5 hours after administration of the correction bolus. In case $PG < 54$ mg/dL, hypoglycemia rescue will be provided. In case $PG > 306$ mg/dL for more than one hour, hyperglycaemia rescue will be provided. Thereafter, subjects will receive a free-choice lunch and a pre-defined evening meal covered by the subject's usual bolus dose.

Day 1 / Day 2: recovery from hyperglycemia after basal insulin suspension

After the insulin bolus given with the evening meal, no correction boli should be given subcutaneously. Overnight, the basal insulin infusion rate will be running and a target fasting plasma glucose level in the range of 126 ± 20 mg/dL will be aimed for. The basal insulin infusion rate will be fixed to a single hourly rate from at least – 3 hours prior to basal insulin suspension. Basal insulin suspension will be performed between 8 and 10 hours after the dinner meal on Day 1. On-site glucose measurements [REDACTED] will be performed regularly and frequently to follow the rise in plasma glucose concentration above 240 mg/dL and blood samples for PK analysis will be taken to analyse the decline in circulating insulin levels. As soon as a glucose measurement above the high glucose threshold has been measured and the result has been confirmed by a second measurement a correction bolus will be administered via a subcutaneous injection in the periumbilical region using an insulin syringe. In addition, a plasma sample for ketone concentration will be taken during this time. Regular and frequent sampling for PK, ketone and glucose analysis continues and the time to reach a $PG \leq 140$ mg/dL will be documented.

After completion of basal insulin suspension procedures at Visit 3 Day 2, subjects will be switched back to their usual diabetes therapy and come back to the trial centre for the final examination.

Up to 28 subjects will be randomised in this trial to ensure that at least approximately 24 subjects complete both the periods to enable evaluation of the primary objective. The subjects will be

Statistical Analysis Plan				
Trial ID	EudraCT-No.	Date	Status / Version-No.	Page
I8B-MC-ITST	2019-003493-13	15 Jul 2020	Final 1.0	14 of 47

randomly allocated to one of two treatment sequences (LY900014 followed by Humalog® or Humalog® followed by LY900014).

[figure not shown]

Figure 1 Study Design

The schedule of assessments performed at each visit is given in [Appendix 1](#).

A description of inclusion and exclusion criteria is given in the protocol Sections 6.2-6.3.

3.2 Investigational Medicinal Products

Subjects will receive LY900014 followed by Humalog® or Humalog® followed by LY900014 as described in [Table 2](#).

Table 2 Treatments administered

IMPs	Strength	Pharmaceutical dosage form	Dose per administration	Route of administration
LY900014	100 U/mL	Solution for injection filled in 3.0 mL pump reservoir/10mL vial	Basal and bolus infusion based on individual needs	subcutaneous infusion via CSII/injection via syringe
Humalog® (insulin lispro)	100 U/mL	Solution for injection filled in 3.0 mL pump reservoir/10mL vial	Basal and bolus infusion based on individual needs	subcutaneous infusion via CSII/injection via syringe

Statistical Analysis Plan				
Trial ID	EudraCT-No.	Date	Status / Version-No.	Page
I8B-MC-ITST	2019-003493-13	15 Jul 2020	Final 1.0	15 of 47

IMPs will be administered subcutaneously in the abdomen by use of:

- an insulin pump (Medtronic MiniMed 640G) and Quick Set[®] (Medtronic, Meerbusch, Germany) infusion sets.
- an insulin syringe

3.3 Planned Number of Participants

Up to 28 subjects will be randomised in this trial to ensure that at least approximately 24 subjects complete both the periods to enable evaluation of the primary objective.

A sample size calculation was performed based on the primary endpoint and an assumption of an SD of the primary endpoint of 78 min (crossover mean square error of ~55). A sample size of 24 subjects who complete the trial is considered to be sufficient to evaluate a difference between the treatments of 32 minutes with a power of 80%. Discontinued subjects may be replaced to ensure that 24 subjects complete the trial. To take account of discontinued subjects, 28 subjects will be randomised in the trial. A replacement subject will be assigned to the same treatment sequence as the subject being replaced.

Subject Replacement:

To account for discontinued subjects (defined as subjects concluding participation, prior to completion of all protocol-required elements after enrollment/ randomisation), up to 28 subjects will be randomised. In case of more than 4 discontinued subjects, four additional replacement subjects may be enrolled (maximum total number of enrolled subjects will not exceed 32 subjects). A replacement subject will be assigned to the same treatment sequence as the subject being replaced.

Screening Failures:

Screened subjects who do not meet or comply with all inclusion and exclusion criteria are excluded (screening failures), and their data will be recorded on a screening failure form. The reason for exclusion must be recorded on the screening failure form. Re-screening of screening failures is generally not allowed.

Planned number of sites:

One site in Germany:

- Profil Institut für Stoffwechselforschung GmbH in Neuss

Statistical Analysis Plan				
Trial ID	EudraCT-No.	Date	Status / Version-No.	Page
I8B-MC-ITST	2019-003493-13	15 Jul 2020	Final 1.0	16 of 47

3.4 Randomisation Code Creation

The Profil Institut für Stoffwechselforschung GmbH, [name], will generate the randomisation codes using the computer program **CCI** [REDACTED] [REDACTED] [REDACTED] [REDACTED]

When a subject is randomised in the study, he/she must always be assigned to the lowest available randomisation number available from the randomisation list. Up to 28 subjects will be randomised to ensure that at least 24 can be evaluated.

Randomisation numbers will be as follows:

- Randomisation numbers starting with 101, 102, 103...

A replacement subject will be assigned to the same treatment as the subject being replaced. For randomisation numbers for replacements 100 will be added to the randomisation number of the subject being replaced.

- Corresponding randomisation numbers for replacements: 201, 202, 203...

Statistical Analysis Plan				
Trial ID	EudraCT-No.	Date	Status / Version-No.	Page
I8B-MC-ITST	2019-003493-13	15 Jul 2020	Final 1.0	17 of 47

4 ANALYSIS VARIABLES

4.1 Demographic and Baseline Characteristics

The following demographic variables and baseline characteristics will be collected at screening:

- Age
- Sex
- Race
- Body Weight, Height, Body mass index (BMI)
- Diabetes duration, diagnosis of diabetes and current diabetes treatment
- Concomitant illness and medical history
- Serology (hepatitis B surface antigen, hepatitis C antibodies and human immunodeficiency virus -1/2 combi)
- Coagulation (International normalized ratio and activated partial thromboplastin time)
- N-(1-deoxy)-fructosyl-haemoglobin (HbA1c)
- Fasting C-Peptide
- Smoking & alcohol habits
- Serum β -HCG (females only)
- Drugs of abuse

The BMI will be calculated based on the height and weight measured at screening according to the following formula:

$$\text{BMI [kg/m}^2\text{]} = \text{weight [kg]} / (\text{height [m]} \times \text{height [m]}).$$

HbA1c will be presented in % as well as in mmol/mol using the following conversion:

$$\text{HbA1c (mmol/mol)} = [\text{HbA1c (\%)} - 2.15] * 10.929.$$

Diabetes duration in years will be calculated as difference between year of informed consent was signed and year of diabetes diagnosis.

A medical history is a condition that started and ended prior to when the informed consent form (ICF) is signed. Concomitant illnesses present at the start of the trial and relevant medical conditions, which deemed to be relevant by the Investigator, will be recorded in the electronic case report form (eCRF) at screening. The information collected for concomitant illness and medical history should include diagnosis, date of onset, date of resolution or continuation.

Any change to a concomitant illness should be recorded during the trial, including end date, if applicable. A clinically significant worsening of a concomitant illness must be reported as AE.

Statistical Analysis Plan				
Trial ID	EudraCT-No.	Date	Status / Version-No.	Page
I8B-MC-ITST	2019-003493-13	15 Jul 2020	Final 1.0	18 of 47

For all female participants, a pregnancy test will be performed at the safety laboratory in a blood (serum) sample obtained at the screening visit.

A urine quick test for the presence of drugs of abuse (e.g. amphetamine, barbiturates, benzodiazepines, cannabis, cocaine, methadone, methamphetamine, opiates, phencyclidine and tricyclic antidepressants) will be performed at the trial site from at least 5 mL fresh mid-stream urine using a stick.

4.2 Assessments for Pharmacokinetics

Eli Lilly will be responsible for the derivation of the PK endpoints and will provide the derived PK endpoints to Profil Institut für Stoffwechselforschung GmbH, Neuss, Germany.

Subjects have measurable insulin lispro concentrations will be included in the analysis dataset for the PK analyses. PK analyses will be conducted using standard noncompartmental methods of analysis (Phoenix[®] version 6.3 or above) on a computer that meets or exceeds the minimum system requirements for these programs. It is possible that other validated equivalent PK software programs may be utilized if appropriate, warranted, and approved by global PK management. The version of any software used for the analysis will be documented, and the program will meet the Lilly requirements of software validation.

Free serum insulin lispro concentrations will be used to calculate several PK parameters including: time to early half-maximal drug concentration (early 50% t_{max}), maximum observed drug concentration (C_{max}), time to maximum observed drug concentration (t_{max}), AUC from time 0 to 15 minutes ($AUC_{(0-15min)}$), AUC from time 0 to 30 minutes ($AUC_{(0-30min)}$), and AUC from time zero to 5 hours ($AUC_{(0-300min)}$). Other parameters may be calculated as deemed appropriate, such as partial AUCs, time to late half-maximal drug concentration (late 50% t_{max}) and AUC from time zero to infinity ($AUC_{(0-\infty)}$), etc.

For Day 1 (Missed Bolus following Meal): The PK parameters will be calculated using change from baseline (CFBL), which is defined as the bolus dose administration (B). For each day and period, the average of the two samples collected immediately prior to the correction bolus will represent the 0-min time point for each subject and will be used to subtract the baseline value from all post-dose insulin lispro measurements. The CFBL PK parameters would include: CFBL AUCs and C_{max} .

For Day 2 (Basal insulin suspension): As each subject will suspend their own individual basal rate, insulin lispro concentration at the time of administration of the correction bolus may vary from being detectable to undetectable (<LLOQ). Due to this, the PK parameters will be

Statistical Analysis Plan				
Trial ID	EudraCT-No.	Date	Status / Version-No.	Page
I8B-MC-ITST	2019-003493-13	15 Jul 2020	Final 1.0	19 of 47

calculated using the CFBL insulin lispro concentrations following the correction bolus (as described in the Day 1 analysis). An analysis using the raw insulin lispro concentration may be explored, if differences in insulin lispro concentration between treatments (LY900014 and Humalog®) prior to the correction bolus are observed.

Additionally, an exploratory analysis may be conducted to assess the insulin lispro PK during the basal insulin suspension to hyperglycemia on Day 2. PK parameters that may be explored include the half-life ($t_{1/2}$) and apparent clearance (CL/F). The insulin lispro concentration time profile may be compared between LY900014 and Humalog® during this time.

Although attempts will be made to adhere to the scheduled collection times, it is recognized that situations arise that may compromise sample collection at the scheduled times. Parameters will be individually calculated for each subject based on actual collection times and presented by summary statistics.

4.3 Assessments for Pharmacodynamics

Eli Lilly will be responsible for the derivation of the PD endpoints and will provide the derived PD endpoints to Profil Institut für Stoffwechselforschung GmbH, Neuss, Germany.

For each study day (Day 1: meal test procedure with missed meal bolus and Day 2: basal insulin suspension), the primary endpoint time to recovery from hyperglycemia after administration of a correction bolus will be determined per subject and period. The determination of the time to recovery after administration of a correction bolus will be calculated from the time of correction bolus administration until the time of the exact point of time when PG is 140 mg/dL, which will be determined using linear interpolation.

Similarly, for each study day, the key secondary PD endpoints include: glucose AUCs, PG_{max} and rate of change in PG will be determined.

The secondary endpoint rate of change in PG will be defined as the change in PG at the time of bolus IMP administration (B) to PG at 140 mg/dl divided by the duration of time for this interval, based on individual measurements per subject, period and day.

The following secondary GD AUCs will be calculated per patient, period and day:

- the area under the PG curve, but above 140 mg/dL from time of correction bolus to the time that the PG is 140mg/dl ($AUC_{B-1PG140}$) and

Statistical Analysis Plan				
Trial ID	EudraCT-No.	Date	Status / Version-No.	Page
I8B-MC-ITST	2019-003493-13	15 Jul 2020	Final 1.0	20 of 47

- the area under the PG curve but above 180mg/dL from time of the correction bolus to the time that the PG is 180mg/dl ($AUC_{B-tPG180}$).

The AUCs will be calculated using the linear trapezoidal rule and using the actual times along with the time when PG is 140 mg/dL or 180mg/dL, which will be determined using linear interpolation. Additionally, calculation of baseline corrected AUC (iAUCs) using the PG at the administration time of the correction bolus may be explored to address possible inter-occasion variability.

The secondary GD endpoint PG_{max} will be determined individually per subject, period and day based on measured PG values.

4.4 Exploratory Endpoints

Evaluation of the exploratory endpoint time to hyperglycemia after basal insulin suspension will be performed on Day 2. The time will be calculated using the time of the basal insulin suspension until the time of the exact point of intersection with the target margin of 240 mg/dL.

The ketone concentration will be measured on Day 2. The peak of ketone concentration will be defined as the maximum of the measured ketone concentrations.

4.5 Safety Endpoint

4.5.1 Adverse Events

An AE is any untoward medical occurrence in a trial subject administered an IMP and which does not necessarily have a causal relationship with the treatment. An AE can therefore be any unfavourable and unintended sign (for example, an abnormal laboratory finding), symptom, or disease temporally associated with the use of an IMP, whether or not considered related to the IMP.

Note: This includes events that occur after the subject has signed the informed consent.

AEs include:

- A clinically significant worsening of a concomitant illness.
- A clinical laboratory abnormality which is clinically significant, i.e. any abnormality that suggests a disease and/or organ toxicity and is of a severity that requires active management. Active management includes active treatment or further investigations, for example change of medicine dose or more frequent follow-up due to the abnormality.

Statistical Analysis Plan				
Trial ID	EudraCT-No.	Date	Status / Version-No.	Page
I8B-MC-ITST	2019-003493-13	15 Jul 2020	Final 1.0	21 of 47

A Treatment Emergent Adverse Event (TEAE) is an AE that emerges during treatment, having been absent pretreatment, or worsens relative to the pretreatment state. In this trial, AEs occurring from first dosing (basal rate) until the follow-up visit will be considered as treatment emergent.

A serious adverse event (SAE) is any untoward medical occurrence that at any dose:

- results in death
- is life-threatening
- requires inpatient hospitalisation or prolongation of existing hospitalisation,
- results in persistent or significant disability or incapacity,
- is a congenital anomaly or birth defect,
- or events that may require intervention to prevent one of the above listed outcomes.

Severe hypoglycaemia will be regarded as SAE and will be recorded on AE and SAE forms.

Suspected Unexpected Serious Adverse Reactions (SUSAR)

An AE, fulfilling one of the criteria of seriousness and being assessed as related to IMP application, the nature or severity of which is not consistent with the applicable reference document (e.g. IB for an unapproved investigational product or package leaflet/SmPC for an approved product).

Other Significant Adverse Events

Other significant adverse events will be defined as marked haematological and other laboratory abnormalities (other than those meeting the definition of serious) and any events that led to an intervention, including withdrawal of test drug/investigational product treatment, dose reduction, or significant additional concomitant therapy, other than those reported as serious adverse events (2).

The maximum intensity (severity) of all AEs must be assessed by the investigator and documented. Severity will be graded when the AE outcome is known:

- Mild
- Moderate
- Severe

A 'severe' reaction does not necessarily deem the AE as 'serious' and a SAE may not be 'severe' in nature.

The causality relationship to study treatment and study procedure of each AE will be assessed by the Investigator according to the following classification:

Statistical Analysis Plan				
Trial ID	EudraCT-No.	Date	Status / Version-No.	Page
I8B-MC-ITST	2019-003493-13	15 Jul 2020	Final 1.0	22 of 47

- Probable
- Possible
- Unlikely

The outcome of all AEs must be assessed by the Investigator and documented by his/her staff.

The following definitions will be used:

- Recovered/resolved
- Recovering/resolving
- Recovered/resolved with sequelae
- Not recovered/not resolved
- Fatal
- Unknown

AE information will include the following:

- AE term
- Date and time of onset and resolution
- Seriousness
- Severity
- Causal relationship to IMP
- Interruption or withdrawal of treatment with IMP and other measures taken
- Outcome

All AEs will be coded using the Medical Dictionary for Regulatory Activities (MedDRA); details are described in the trial specific Data Management Plan.

Missing date and time data will only be replaced if at least the year exists and will be replaced as follows:

- AE start date and time:
 - Month: 1 (January)
 - Day: 1
 - Hour: 0
 - Minute: 0
 - Second: 0
- AE stop date and time:
 - Month: 12 (December)
 - Day: 28, 29, 30 or 31 (last day of the month in the given year)

Statistical Analysis Plan				
Trial ID	EudraCT-No.	Date	Status / Version-No.	Page
I8B-MC-ITST	2019-003493-13	15 Jul 2020	Final 1.0	23 of 47

- Hour: 23
- Minute: 59
- Second: 59

Imputed dates and times will be within the time window from earliest possible start date/time to last possible end date/time. Imputed dates/times outside this time window must be adapted by earliest possible start date/time and last possible end date/time.

If the year is missing, then the date will not be imputed.

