5.10.1 Analysis of Adverse Events

All AEs will be presented by individual listings and non-hypoglycaemic TEAEs (TEAEs in this section are non-hypoglycaemic; severe hypoglycaemia will be taken in account) will be presented using summary tables by treatment. The following summary tables will be presented:

(1) Overview of Incidence of TEAEs including:

- Number of subjects at risk
- Incidence and number of TEAEs
- Incidence of deaths
- Incidence and number of serious TEAEs
- Incidence and number of other significant TEAEs
- Incidence and number of severe TEAEs
- Incidence and number of drug related TEAEs (possibly or probably related to IMP as judged by the investigator)

The presentation will be done by treatment.

(2) TEAEs by MedDRA system organ class (SOC) and preferred term within each SOC and preferred term as well as in total including incidence and number of TEAEs. The presentation will be done by treatment. SOC and preferred terms will be presented in alphabetic order.

(3) TEAEs by SOC and preferred term and by severity, relationship, seriousness, outcome, action taken with study drug due to this TEAE and other action due to this TEAE. The presentation will be done by treatment. SOC and preferred terms will be presented in alphabetic order. Within each category the presentation will be done from the lowest to the highest subcategory.

(4) Separate tables for SAEs (in case of more than 2 SAEs).

The incidence of TEAEs will be presented with the number and percentage of participants affected. Percentages will be derived as ratio of number of participants affected and number of participants at risk multiplied by 100.

The following will be included in the listing of AEs:

- Screening and randomisation number
- Gender, age, race and weight

Statistical Analysis Plan				
Trial ID	EudraCT-No.	Date	Status / Version-No.	Page
I8B-MC-ITST	2019-003493-13	15 Jul 2020	Final 1.0	34 of 47

- Event number
- Treatment
- SOC and PT term
- Event term
- Start date and time
- End date and time
- Last dose date and time
- Seriousness
- Severity
- Outcome
- Relationship to IMP
- Relationship to study device
- Action taken with study drug due to this AE
- Action taken with device
- Other action taken due to this AE
- Time since last dosing and duration

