APPENDIX 2 – ASSESSMENT SCHEDULE (FOR VISITS 2 AND 3)

Approx. hour	Nominal timing	Activity	Insulin (PK)	Plasma glucose ¹	Other
Day -1 17:00		Subject arrives at the trial site and continued eligibility will be checked		X	Dosing visit exclusion criteria, AEs, concomitant medication, alcohol breath test, vital signs, ECG, physical examination, urine pregnancy test, weight ⁴
17:30		Randomization (Visit 2 only) Discontinue subject's own insulin pump if not using Medtronic 640G; insert new infusion set; Start study insulin pump with IMP (subject's usual basal rate)			
18:00		Pre-defined evening meal Covered by individual meal bolus		X	
Day 1 04:00		START overnight stabilisation i.v. insulin glulisine or glucose infusion (if needed) Morning plasma glucose target (126 ± 20 mg/dL) ⬇		Sampling approx. every 30 min. or more frequently, if needed	
05:00		Fixed basal rate (single hourly rate) of CSII from at least -3 h until end of meal test (B + 5 h) ⬇		⬇	
07:30	-30 min	STOP i.v. insulin or glucose infusion (if any) Maintain PG at in the range of 126 ± 20 mg/dL			
Day 1 08:00	0	Standard liquid meal	X (pre-meal)	X (pre-meal)	Dosing visit exclusion criteria, AEs, concomitant medication
	15min	Liquid meal fully consumed		X	
	30min	Plasma glucose measurement: every 10 minutes if $PG \leq 200$ mg/dL and every 5 minutes if $PG > 200$ mg/dL ⬇		X ⬇	
	B ²	Confirmatory glucose measurement if $PG > 240$ mg/dL, followed by pump correction bolus	X ³	X ³	
	B + 5min		X	X	
	B + 10min		X	X	
	B + 15min		X	X	
	B + 20min		X	X	
	B + 25min		X	X	

Statistical Analysis Plan				
Trial ID	EudraCT-No.	Date	Status / Version-No.	Page
I8B-MC-ITST	2019-003493-13	15 Jul 2020	Final 1.0	46 of 47

Approx. hour	Nominal timing	Activity	Insulin (PK)	Plasma glucose ¹	Other
	B + 30min	As soon as PG ≤ 140 mg/dL is measured, a confirmatory PG is performed	X	X	
	B + 35min		X	X	
	B + 40min		X	X	
	B + 45min		X	X	
	B + 50min		X	X	
	B + 55min		X	X	
	B + 1h		X	X	
	B + 65min			X	
	B + 70min		X	X	
	B + 75min			X	
	B + 80min			X	
	B + 85min			X	
	B + 90min		X	X	
	B + 95min			X	
	B + 100min			X	
	B + 105min		X	X	
	B + 110min			X	
	B + 115min			X	
	B + 2h	If PG > 140 mg/dL, PG sampling will continue every 5 minutes If PG ≤ 140 mg/dL, PG sampling will be every 15 minutes	X	X	
	(B + 125 min)	If PG > 140 mg/dL		(X)	
	(B + 130min)	If PG > 140 mg/dL		(X)	
	B + 135min		X	X	
	(B + 140min)	If PG > 140 mg/dL		(X)	
	(B + 145min)	If PG > 140 mg/dL		(X)	
	B + 150min		X	X	
	(B + 155min)	If PG > 140 mg/dL		(X)	

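### The SAP fills missing parts of an AE start with the earliest values, under a lower limit it never defines, so an AE that began on IMP can be dated before it

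*SAP*

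**What the plan says.** SAP 4.5.1 introduces its rule for incomplete AE dates with: "Missing date and time data will only be replaced if at least the year exists and will be replaced as follows". For a start, the values are January, day 1 and 00:00:00. For a stop, they are December, the last day of the month and 23:59:59. Two sentences then limit the result: "Imputed dates and times will be within the time window from earliest possible start date/time to last possible end date/time" and "Imputed dates/times outside this time window must be adapted by earliest possible start date/time and last possible end date/time". The section ends: "If the year is missing, then the date will not be imputed". The SAP does not say whether the lower limit is consent, first IMP or the start of the treatment period.

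The same section defines treatment emergence: "AEs occurring from first dosing (basal rate) until the follow-up visit will be considered as treatment emergent". Under Protocol 9.2, AEs are collected from informed consent. SAP Appendix 2 and Protocol Table 2 place this step at about 17:30 on Day -1 of each period: "Start study insulin pump with IMP". On the TEAE tables, SAP 5.10.1 says: "The presentation will be done by treatment".

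The SAP has no rule of its own for allocating AEs to a product. Protocol 13.4.4 allocates them from pump start to pump disconnection on Day 2. It puts pump start on Day 1, although the schedule puts it on Day -1.

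**The concern.** Whether an AE is treatment-emergent, and which product it counts against, depends on whether it began before or after a pump start. When the record cannot settle that order, the default picks the earliest moment the known parts allow. For an onset close to a pump start, that moment lies before it. The usual cautious choice in safety analysis is the opposite: an onset that cannot be shown to precede treatment counts as treatment-emergent.

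AEs are the only named safety endpoint (Protocol 4.2.4; SAP Table 1), and the AE summary tables cover only TEAEs. An AE wrongly dated before first IMP would leave those tables. One wrongly dated before the second product would not be counted against the product on which it began.

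**Working it through.** The plan gives no figure to reproduce, so the check applies its rule to cases.

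**1. Does a consent limit catch the default?** Consent is at least 1 day before screening, and screening is 1–28 days before Visit 2 (SAP 3.1). Midnight at the start of Visit 2 Day -1 is therefore after consent, inside the window, and left unchanged.

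**2. Missing time on Day -1.** The default is 00:00 and the pump starts at about 17:30. The imputed start is 17:30 − 00:00 = 17.5 h before IMP. The stretch of that day spent on IMP is 24:00 − 17:30 = 6.5 h, and an onset in it with no recorded time is dated before IMP.

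**3. Missing day in the month of first dosing.** The default is 00:00 on the 1st, or consent if later. Both precede first IMP.

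**4. Eight test AEs.** The calendar is an assumption that fits the visit windows: consent 2 March 2020 09:00, first IMP 16 March 17:30, second product 23 March 17:30. All eight truly began on IMP.

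| Test AE: true onset, missing parts | Default start | Limit = consent | Limit = first IMP | Limit = IMP start of true period |
|---|---|---|---|---|
| A: 16 Mar 20:00, time | 16 Mar 00:00 | pre-treatment | period 1 | period 1 |
| B: 17 Mar 10:00, time | 17 Mar 00:00 | period 1 | period 1 | period 1 |
| C: 17 Mar 10:00, day and time | 1 Mar 00:00 | pre-treatment | period 1 | period 1 |
| D: 17 Mar 10:00, month, day and time | 1 Jan 00:00 | pre-treatment | period 1 | period 1 |
| E: 23 Mar 20:00, time | 23 Mar 00:00 | between periods | between periods | period 2 |
| F: 24 Mar 10:00, time | 24 Mar 00:00 | period 2 | period 2 | period 2 |
| G: 24 Mar 10:00, day and time | 1 Mar 00:00 | pre-treatment | period 1 | period 2 |
| H: 24 Mar 10:00, month, day and time | 1 Jan 00:00 | pre-treatment | period 1 | period 2 |

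- **No limit, or consent:** 5 of 8 pre-treatment (A, C, D, G, H) and 6 of 8 misassigned in all (E added).
- **First IMP:** 0 pre-treatment and 3 misassigned (G and H to period 1, E to the gap between periods).
- **IMP start of the true period:** 0 and 0. This presupposes the period, which G and H do not record.

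**5. The proposed rule on the same cases, with no stop before IMP start.** A becomes 16 March 17:30 and E becomes 23 March 17:30, both correct. B and F are unchanged and correct. C, D, G and H fit both periods, so they are treatment-emergent, placed in period 1 and flagged. The result is 0 of 8 pre-treatment. In the main table 2 of 8 (G, H) are in the wrong period. The sensitivity table moves all four flagged AEs to period 2, which corrects G and H and displaces C and D. The recorded data cannot separate these four.

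These cases show how the rule behaves. They do not estimate how often it matters.

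**The case against.** The strongest reply is that the lower limit could mean first IMP. Nothing in the SAP forbids this, and it removes every pre-treatment error in the test cases. It is not written down, however, and it still leaves the shift away from the second product.

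The second reply is that the damage is small and visible. Onset date and time are recorded for every AE (Protocol 9.2), queries must be resolved (Protocol 9.3), and the dosing periods are in-house. Imputed values are flagged in listings (SAP 5.4), and all AEs are listed individually (SAP 5.10.1, with hypoglycaemia listed separately under 5.10.2). Hypoglycaemia has its own form and tables and enters the TEAE tables only if severe. All of this stands. It limits the effect, but a listing does not correct a summary table.

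A reader might also infer three stronger things that the documents do not support:

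- **That every on-IMP AE with a partial date is misclassified.** Only missing parts are replaced. Test AEs B and F keep their class under every reading.
- **That the rule can only move AEs away from treatment.** An AE after pump disconnection on Day 2 with no time is set to 00:00 that day, inside the allocation window of Protocol 13.4.4.
- **That the rule favours LY900014.** Sequence is randomised, so each product comes second in one of the two sequences.

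**Conclusion.** The point holds in limited form. With consent as the lower limit, the stated rule can remove from the TEAE tables an AE that began on IMP on Visit 2 Day -1, or in the month of first dosing, when its time or day is missing. It can also date a Visit 3 Day -1 AE before the second product. Where the order of onset and first dose cannot be told, this is the less cautious choice.

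The conclusion rests on reading the undefined limit as consent, which the AE collection period makes natural but the SAP does not state. If the limit is first IMP, only the shift between periods remains. The documents give no rate of incomplete dates, so the effect cannot be sized. It is probably small, and no bias between products is shown.

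**What to change.** Amend SAP 4.5.1 as follows:

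- Replace missing parts only, and never change a known part.
- If the known parts of the start match the date (or the month or year) of IMP start in a period, so that the order cannot be told, and the stop is not before that IMP start, impute the start as that IMP start date and time. The AE is then treatment-emergent.
- If the known parts already place onset on an earlier or later date, keep the present rule, and say what its lower limit is.
- If the known parts fit both periods, count the AE as treatment-emergent, assign it to the earliest compatible period and flag it in the listing. Repeat the by-treatment TEAE table with it assigned to the other period, as a sensitivity check.
- Leave stop-date imputation unchanged.

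The cost is a few sentences, a few lines of program and one extra table if any AE is flagged. The downside is that a few truly pre-treatment AEs may be counted as TEAEs.
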